4.5 Selection and Timing of Dose for Each Subject

Each subject will receive a single IV dose of either 10 mg/kg belatacept Process E or 10 mg/kg belatacept Process C infused over 30 minutes on Day 1.

4.6 Blinding/Unblinding

Not applicable.

4.7 Treatment Compliance

Study drug will be administered intravenously in the study site under the supervision of study personnel.

4.8 Destruction of Study Drug

For this study, study drugs (those supplied by BMS or sourced by the investigator) such as partially used study drug containers, vials and syringes may be destroyed on site.

Any unused study drugs can only be destroyed after being inspected and reconciled by the responsible BMS study monitor unless study drug containers must be immediately destroyed as required for safety, or to meet local regulations (eg, cytotoxics or biologics).

On-site destruction is allowed provided the following minimal standards are met:

- On-site disposal practices must not expose humans to risks from the drug.
- On-site disposal practices and procedures are in agreement with applicable laws and regulations, including any special requirements for controlled or hazardous substances.
- Written procedures for on-site disposal are available and followed. The procedures must be filed with the site's standard operating procedures and a copy provided to BMS upon request.
- Records are maintained that allow for traceability of each container, including the date disposed of, quantity disposed, and identification of the person disposing the containers. The method of disposal, (ie, incinerator, licensed sanitary landfill, or licensed waste disposal vendor) must be documented.
- Accountability and disposal records are complete, up-to-date, and available for the monitor to review throughout the clinical trial period.

If conditions for destruction cannot be met the responsible BMS study monitor will make arrangements for return of study drug.

It is the investigator's responsibility to arrange for disposal of all empty containers, provided that procedures for proper disposal have been established according to applicable federal, state, local, and institutional guidelines and procedures, and provided that appropriate records of disposal are kept.

4.9 Return of Study Drug

If study drug will not be destroyed upon completion or termination of the study, all unused and/or partially used study drug that was supplied by BMS must be returned to BMS. The return of study drug will be arranged by the responsible study monitor.

It is the investigator's responsibility to arrange for disposal of all empty containers, provided that procedures for proper disposal have been established according to applicable federal, state, local, and institutional guidelines and procedures, and provided that appropriate records of disposal are kept.

4.10 Retained Samples for Bioavailability/Bioequivalence

Not applicable.

5. STUDY ASSESSMENTS AND PROCEDURES

5.1 Flow Chart/Time and Events Schedule

Study assessments and procedures are presented in [Table 5.1-1](#) and [Table 5.1-2](#).

Table 5.1-1: Screening Procedural Outline (IM103349)

Procedure	Screening Visit Day -28 to Day -2	Day -1 Visit	Notes
Eligibility Assessments			
Informed Consent	X		A subject is considered enrolled only when a protocol-specific informed consent is signed.
Inclusion/Exclusion Criteria	X	X	
Medical History	X		Include any toxicities or allergy related to previous treatments. Screening medical history evaluation may occur on Day -1 if the screening physical examination occurs on Day -1 (See "Physical Examination" note below).
Admit to Clinical Facility		X	
Safety Assessments			
Physical Examination	X	X	If the screening physical examination is performed within 24 hours prior to dosing on Day 1 then a single examination may count as both the screening and prior to dosing evaluation.
Physical Measurements	X	X	Height and weight at screening; weight only Day -1. Body mass index will be calculated at screening and on Day -1.
Vital Signs	X	X	Includes body temperature, respiratory rate, and seated blood pressure and heart rate. Blood pressure and heart rate should be measured after the subject has been resting quietly for at least 5 minutes. Day -1 vital sign measurements must be reviewed prior to dosing on Day 1.
12-Lead ECGs	X	X	ECGs should be recorded after the subject has been supine for at least 5 minutes. Results must be reviewed prior to dosing on Day 1.
Chest X-ray	X		A posterior-anterior and lateral chest x-ray will be performed at enrollment. A chest x-ray performed within the past 6 months will be acceptable provided written documentation of negative results is available.
Laboratory Tests	X	X	Includes blood and urine samples. Subjects are required to fast for at least 10 hours prior to the collection of specimens for clinical laboratory tests. All clinical laboratory assessment must be available and reviewed by the investigator prior to dosing on Day 1.

Table 5.1-1: Screening Procedural Outline (IM103349)

Procedure	Screening Visit Day -28 to Day -2	Day -1 Visit	Notes
Serology	X		Includes hepatitis C antibody, hepatitis B surface antigen, and HIV-1 and -2 antibodies. Results must be available and reviewed prior to dosing on Day 1.
QuantiFERON-TB Gold Test	X		A QuantiFERON-TB Gold test performed within 4 weeks of dosing on Day 1 will be acceptable.
Urine Drug Test (including cotinine)	X	X	Results must be available and reviewed prior to dosing on Day 1.
Alcohol Test	X	X	A urine alcohol test will be performed. Results must be available and reviewed prior to dosing on Day 1.
Pregnancy Test	X	X	For WOCBP only; serum pregnancy test at screening and Day -1. Serum or urine pregnancy test at all subsequent time points during the study. Results must be reviewed prior to dosing on Day 1.
Follicle-stimulating Hormone			Women only. Refer to Section 3.3.3 .
Adverse Event Reporting			
Monitor for Serious Adverse Events	X	X	All SAEs must be collected from the date of subject's written consent until 30 days after discontinuation of dosing or completion of the subject's participation in the study if the last scheduled visit occurs at a later time.

Abbreviations: ECG = electrocardiogram; HIV = human immunodeficiency virus; SAEs = serious adverse events; WOCBP = women of childbearing potential.

Table 5.1-2: On Treatment Procedural Outline (IM103349)

Procedure ^a	Day 1	Day 2	Day 4 ^b	Day 8	Day 15	Day 22	Day 29	Day 36	Day 43	Day 57	Day 71 ^c	Notes
Safety Assessments												
Physical Examination			X								X	
Physical Measurements											X	Weight only
Vital Signs	X		X		X		X		X		X	Vital signs will be measured predose and within 30 minutes postdose on Day 1. Day 4 vital signs will be measured prior to furlough from study site. See note in screening procedures.
12-Lead ECG											X	See note in screening procedures.
Laboratory Tests			X		X			X			X	See note in screening procedures and Section 5.3.2 .
Pregnancy Test			X				X			X	X	
Adverse Event Reporting												
Monitor for Nonserious AEs	X	X	X	X	X	X	X	X	X	X	X	AEs will be reported from after dose of study drug through Day 71.
Monitor for SAEs	X	X	X	X	X	X	X	X	X	X	X	SAEs will be reported from subject's written consent through Day 101.
Pharmacokinetic (PK) Assessments												
Serial Blood PK Sampling for Belatacept	X	X	X	X	X	X	X	X	X	X		See Table 5.5.1-1 .

Table 5.1-2: On Treatment Procedural Outline (IM103349)

Procedure ^a	Day 1	Day 2	Day 4 ^b	Day 8	Day 15	Day 22	Day 29	Day 36	Day 43	Day 57	Day 71 ^c	Notes
Immunogenicity Assessments												
Blood Sampling	X				X		X		X	X	X	Prior to dosing on Day 1. See Table 5.5.1-1 . Subjects who seroconvert and continue to have a high titer at study discharge that is considered to be significantly increased versus baseline will be asked to return for follow-up assessment(s) for anti-belatacept antibodies approximately every 4 months until their titers and/or sero-status are judged to be stable by the investigator.
Clinical Drug Supplies												
Randomize	X											
Study Drug Administration	X											Supplied by BMS.

Abbreviations: AE = adverse event; ECG = electrocardiogram; PK = pharmacokinetic; SAE = serious adverse event.

^a The window for Days 8 and 15 is \pm 1. The window for Days 22, 29, 36, 43, and 57 is \pm 2. The window for Day 71 is -2 days.^b Subjects will be furloughed from the clinic site after the Hour 72 PK sample on Day 4.^c Evaluations performed prior to study discharge, or for subjects who are prematurely discontinued.

In the event multiple procedures are required at a single time point, the following is a list of procedures from highest priority to low:

- 1) PK sampling
- 2) Safety (ECG)
- 3) Safety (clinical laboratory tests)

5.1.1 *Retesting During Screening or Lead-in Period*

Retesting of laboratory parameters and/or other assessments within any single screening or lead-in period will be permitted (in addition to any parameters that require a confirmatory value).

Any new result will override the previous result (ie, the most current result prior to enrollment) and is the value by which study inclusion will be assessed, as it represents the subject's most current, clinical state.

Laboratory parameters and/or assessments that are included in [Table 5.1-1](#) may be repeated in an effort to find all possible well-qualified subjects. Consultation with the medical monitor may be needed to identify whether repeat testing of any particular parameter is clinically relevant.

5.2 *Study Materials*

The site will provide all required materials for the tests performed locally (ie, relevant clinical laboratory tests and urine drug screens). The site will have available a well-calibrated scale for recording body weight, a 12-lead ECG machine, and a calibrated sphygmomanometer and thermometer for vital signs assessments. A current and fully-stocked advanced cardiac life support cart will be immediately available on the premises. The site will have, a refrigerated centrifuge, a monitored and alarmed refrigerator, and freezer (-20°C [-68°F] or below), as well as containers and dry ice for shipment and storage of blood samples. The site will provide all materials required for accurate source documentation of study activities and for housing the subjects during the study. The site will source marketed product from a single commercial lot.

BMS or designee will provide a BMS-approved protocol and any amendments or administrative letters (if required), and IB. Case report forms (electronic or hard copy) will be provided by BMS or designee. BMS or the clinical facility will provide labels and tubes for the collection of blood samples for PK and immunogenicity analysis.

5.3 *Safety Assessments*

5.3.1 *Imaging Assessment for the Study*

Any incidental findings of potential clinical relevance found on a chest x-ray that are not directly associated with the objectives of the protocol should be evaluated and handled by the study investigator as per standard medical/clinical judgment.

5.3.2 *Laboratory Test Assessments*

A local laboratory will perform the analyses and will provide reference ranges for these tests. Results of clinical laboratory tests performed on Day -1 must be available prior to dosing.

The following clinical laboratory tests will be performed:

Hematology

Hemoglobin
Hematocrit
Total leukocyte count, including differential
Platelet count

Serum Chemistry

AST	Fasting glucose
ALT	Total protein
Total bilirubin	Albumin
Direct bilirubin	Sodium
Alkaline phosphatase	Potassium
Lactate dehydrogenase	Chloride
Creatinine	Calcium
Blood urea nitrogen	Phosphorus
Uric acid	Magnesium

Urinalysis

Protein
Glucose
Blood
Leukocyte esterase
Specific gravity
pH

Microscopic examination of the sediment if blood, protein or leukocytes esterase are positive on the dipstick

Serology

Serum for hepatitis C antibody, hepatitis B surface antigen, HIV-1 and -2 antibody (screening only)

Other Analyses

Test for drugs of abuse, including cotinine (urine or serum) (screening and Day -1)

Alcohol screening (urine) (screening and Day -1)

FSH (if necessary for confirmation of menopause at screening; see [Section 3.3.3](#)).

Pregnancy test (WOCBP only: screening, Day -1, Days 4, 29, 57, and 71)

QuantiFERON-TB Gold test (screening only)

Results of all laboratory tests required by this protocol must be provided to BMS, either recorded on the laboratory pages of the CRF or by another mechanism as agreed upon between the investigator and BMS (eg, provided electronically). If the units of a test result differ from those printed on the CRF, the recorded laboratory values must specify the correct units. Any abnormal laboratory test result considered clinically significant by the investigator must be recorded on the appropriate AE page of the CRF (See [Section 6.3](#)).

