Abbreviations: E = enrollment; IMG = immunogenicity; IV = intravenous; PK = pharmacokinetic; R = randomization; S = screening.

^a Subjects randomly assigned within stratified weight categories in a 1:1 ratio.

^b Subjects will return to the study site for collection of a single PK sample.

^c Evaluations performed prior to study discharge, or for subjects who are prematurely discontinued.

Physical examinations, vital sign measurements, 12-lead ECGs, and clinical laboratory evaluations will be performed at selected times throughout the study. Subjects will be closely monitored for AEs throughout the study. Approximately 200 mL of blood will be drawn from each subject during the study.

The approximate duration of the study is a 28-day screening period, 71 study days per subject for a total of up to 99 days.

Subjects who seroconvert and continue to have a high titer at study discharge that is considered to be significantly increased versus baseline will be asked to return for follow-up assessment(s) for anti-belatacept antibodies approximately every 4 months until their titers and/or sero-status are judged to be stable by the investigator.

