6.1.1 Serious Adverse Event Collection and Reporting

Sections 5.6.1 and 5.6.2 in the IB represent the Reference Safety Information to determine expectedness of SAEs for expedited reporting. Following the subject's written consent to participate in the study, all SAEs, whether related or not related to study drug, must be collected, including those thought to be associated with protocol-specified procedures. All SAEs must be collected that occur during the screening period and within 101 days of discontinuation of dosing.

The investigator must report any SAE that occurs after these time periods and that is believed to be related to study drug or protocol-specified procedure.

An SAE report must be completed for any event where doubt exists regarding its seriousness.

If the investigator believes that an SAE is not related to study drug, but is potentially related to the conditions of the study (such as withdrawal of previous therapy or a complication of a study procedure), the relationship must be specified in the narrative section of the SAE Report Form.

SAEs, whether related or not related to study drug, and pregnancies must be reported to BMS or designee within 24 hours of awareness of the event. SAEs must be recorded on the SAE Report Form; pregnancies on a Pregnancy Surveillance Form (electronic or paper forms). The preferred method for SAE data reporting collection is through the electronic case report form (eCRF). The paper SAE/pregnancy surveillance forms are only intended as a back-up option when the eCRF system is not functioning. In this case, the paper forms are to be transmitted via email or confirmed facsimile (fax) transmission to:

SAE Email Address: Refer to Contact Information list.

SAE Facsimile Number: Refer to Contact Information list.

For studies capturing SAEs through electronic data capture, electronic submission is the required method for reporting. In the event the electronic system is unavailable for transmission, paper forms must be used and submitted immediately. When paper forms are used, the original paper forms are to remain on site.

SAE Telephone Contact (required for SAE and pregnancy reporting): Refer to Contact Information list.

If only limited information is initially available, follow-up reports are required. (Note: Follow-up SAE reports must include the same investigator term(s) initially reported).

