8.4.3 Safety Analyses

All recorded AEs will be listed and tabulated by system organ class, preferred term, and treatment. Vital signs and clinical laboratory test results will be listed and summarized by treatment. Any significant physical examination findings, ECG recordings, and clinical laboratory results will be listed. The number and percentage of subjects with marked laboratory abnormalities will be summarized. Electrocardiogram recordings will be evaluated by the investigator and abnormalities, if present, will be listed. All SAEs reported through Day 101 after the dose of the study drug will be included in the SAE summary table. All nonserious AEs that are reported through Day 71 after the dose of the study drug will be included in the AE summary

table. Data from any safety related procedure after Day 71 or nonserious AEs will continue to be collected in the source documents, but not captured in the eCRF.

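### The SAE collection rules do not share one end day, and no routine contact is scheduled between discharge and the Day 101 cut-off of the SAE table

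*Protocol*

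**What the plan says.** The documents state the SAE window in several places.

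- **Protocol Table 5.1-1 (screening schedule, SAE row):** collection starts at consent and runs "until 30 days after discontinuation of dosing or completion of the subject's participation in the study"; the second limb applies when the final planned visit is the later of the two. No day number is given.
- **Protocol Table 5.1-2 (on-treatment schedule, SAE row):** "SAEs will be reported from subject's written consent through Day 101". The last visit marked in that row is Day 71, the discharge visit, which has a window of minus 2 days.
- **Protocol 6.1.1:** "All SAEs must be collected that occur during the screening period and within 101 days of discontinuation of dosing". Later SAEs must still be reported if the investigator believes them related to study drug or a protocol procedure.
- **Protocol 8.4.3 (repeated in the synopsis):** "All SAEs reported through Day 101 after the dose of the study drug will be included in the SAE summary table".
- **SAP 7.6.3:** SAEs after discharge are assigned to the treatment received if reported through Day 101.
- **SAP 7.6.2:** every reported SAE in enrolled subjects is listed and summarised, with no cut-off.

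On dosing and follow-up, Protocol 4.5 says "Each subject will receive a single IV dose of either 10 mg/kg belatacept Process E or 10 mg/kg belatacept Process C", given on Day 1. Protocol 3.1 puts participation at a 28-day screening period plus "71 study days per subject for a total of up to 99 days". After discharge, the only planned contact is a return about every 4 months for subjects who seroconverted and still have a high titer at discharge. That contact is described for antibody assessment.

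**The concern.** Two operative collection rules in the same section of the protocol can be read as ending 30 days apart. A site that works from the Table 5.1-1 note could reasonably close SAE collection at discharge. A site that works from Table 5.1-2 must keep collecting to Day 101, but the schedule gives it no visit or call at which to ask.

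Safety after a single dose is a secondary objective, and the SAE table will be read as covering every subject through Day 101. Protocol Section 6 says adverse events are either reported spontaneously or elicited by questioning, examination or evaluation. For Days 72 to 101 the schedule provides no occasion for the second route. If nothing is recorded in that stretch, the reader cannot tell a subject without an event from a subject who was not asked.

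Pregnancy is affected in the same way. Section 6.1 has pregnancies handled as SAEs, and the contraception commitment for women in 3.3.1 runs 80 days past treatment. With dosing on Day 1 that is Day 81, after the last scheduled contact.

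**Working it through.** **Inputs**

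- Single dose on Day 1, so the end of dosing is Day 1 (Protocol 4.5).
- Day 71 is nominal hour 1680 (Table 5.5.1-1). 1680 / 24 = 70 days after the start of infusion, so Day N is N − 1 days after dosing.
- Discharge is at Day 71 with a window of minus 2 days, so Day 69 to Day 71 (Table 5.1-2).
- SAE table cut-off is Day 101 (Protocol 8.4.3, SAP 7.6.3).

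**Step 1. Where Day 101 comes from.** Thirty days added to completion at Day 71 gives 71 + 30 = Day 101. This reproduces the figure in Table 5.1-2, 8.4.3 and SAP 7.6.3.

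**Step 2. The Table 5.1-1 note, for a subject without antibody follow-up.**

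- Reading A: the later of (dosing + 30 days) and completion of participation. Max(1 + 30, 71) = max(31, 71) = Day 71.
- Reading B: 30 days after the later of dosing and completion. Max(1, 71) + 30 = Day 101.

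Reading A follows the grammar more naturally, because the 30 days are attached to the end of dosing and completion stands as the alternative. Reading B agrees with Table 5.1-2. One sentence thus supports end days 30 days apart. If antibody recall counts as participation, neither reading gives Day 101 for a recalled subject; collection would run on to the end of that follow-up, or 30 days beyond it.

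**Step 3. Section 6.1.1.** The window is "within 101 days of discontinuation of dosing". Counted literally, Day 1 + 101 = Day 102, one day past the table cut-off.

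**Step 4. Time without a routine contact before Day 101.**

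| Last visit | Days to Day 101 | Share of 101 days |
|---|---|---|
| Day 71 | 101 − 71 = 30 | 29.7% |
| Day 69 | 101 − 69 = 32 | 31.7% |

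**Step 5. Does antibody recall fill the gap?** Taking 4 months as 4 × 30.4 days (an assumption), the first recall falls at 71 + 121.6 = 192.6, about Day 193. That is after Day 101, so it could reveal events from Days 72 to 101 only in retrospect, and only in the recalled subjects.

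**The case against.** The strongest reply is that the window is clear and the outlier is a single note in a screening table. Table 5.1-2, 8.4.3, the synopsis and SAP 7.6.3 all say Day 101, and Reading B of the note agrees with them. Section 6.1.1 makes collection mandatory for the whole window and keeps related SAEs reportable afterwards. Section 8.4.3 expects safety data after Day 71 to be kept in source documents, and SAP 6.1 provides for a post-treatment period. The gap applies to both arms and concerns a secondary objective. The SAP background also reports no SAEs in the pooled healthy-volunteer population.

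Much of this stands, and it rules out several stronger inferences that a reader might draw:

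- **That the protocol sets three distinct end points.** Day 71 is nowhere printed as an SAE end day; it is one reading of one sentence. Day 101 against Day 102 is a counting difference of no practical weight.
- **That the SAE table is incomplete by design.** Collection through the window is required. What is missing is a stated means of seeking events after discharge, which supports a risk of under-ascertainment and no more.
- **That most subjects have no contact after Day 71.** High-titer seroconverters are recalled and their share is not given. Protocol 1.4.4.2 puts antibody formation in healthy subjects at up to 100%.
- **That late SAE capture depends materially on antibody status.** The first recall comes after Day 101, so this could act only through retrospective recall.
- **That the 99-day duration contradicts the SAE window.** 28 + 71 = 99 is offered as an approximate length of screening plus study days. It need not include SAE reporting after discharge, which would make it 28 + 101 = 129.

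What the reply does not remove is that an operative rule can be read to stop collection 30 days before the table's cut-off, and that no routine contact is scheduled to support those days.

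**Conclusion.** The point holds as a conflict between collection rules, together with a gap in planned ascertainment. The Table 5.1-1 note most naturally ends collection at Day 71 for a subject without antibody follow-up, against Day 101 in Table 5.1-2, 8.4.3 and SAP 7.6.3. SAP 7.6.2 adds a summary with no cut-off. The period without routine contact is 30 to 32 days, or 29.7% to 31.7% of the 101-day window, and SAEs in it may be under-ascertained in both arms.

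This should be corrected, but its reach is limited. It bears on a secondary safety objective and leaves the AUC(INF) and Cmax comparison untouched. The documents give no basis for saying how many events, if any, would be missed.

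The conclusion assumes that dosing is Day 1, that discharge is completion of participation for a subject without antibody follow-up, and that no contact outside the printed schedule was planned. The Day 193 figure also assumes 30.4-day months.

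**What to change.** 1. Reconcile the Table 5.1-1 note, Table 5.1-2, Protocol 6.1.1 and SAP 7.6.2 to one SAE end day, with one day-counting rule, matching the summary in 8.4.3 and SAP 7.6.3. Say whether antibody recall extends the window.
2. Add to Table 5.1-2 one telephone check on that day, asking about SAEs and pregnancy, for subjects who have not yet passed it.
3. Where no such contact was made, footnote the SAE table to say that events after Day 71 rest on spontaneous reports.
4. Do not truncate the SAE table at Day 71. That would remove reported events and make the output worse.

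The cost is wording changes, one short call per remaining subject, and ethics review of the amendment with possible consent revision under Protocol 9.1.1. The limitation is uneven coverage. SAP Section 1 says 146 of the 176 planned subjects were dosed before Amendment 02, and dosing dates are not given, so some may already be past Day 101. If only the 30 replacements could be called, that would be 30 of the 146 subjects in the summaries (116 + 30), or 20.5%. The footnote is therefore needed even if the call is added.
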